- If the date of last dose + 28 days extends to a date beyond the date of the final visit date (not including SFU), then this calculation reverts to:

$$\text{Date of last visit (not including SFU)} - \text{Date of first dose} + 1$$

- For study participants who die, then this calculation reverts to:

$$\text{Date of death} - \text{Date of first dose} + 1$$

- For study participants who switch study treatments per study design (ie, study participants initially randomized to placebo who are re-allocated to bimekizumab treatment):

- During the DBTP (attributed to initially randomized treatment):

$$\text{Date of last dose (DBTP)} - \text{Date of first dose (DBTP)} + 28$$

Note: If date of last dose in the Initial Period + 28 days extends to a date beyond the date of first dose in the Maintenance Period, then this calculation reverts to:

$$\text{Date of first dose (MP)} - \text{Date of first dose (DBTP)} + 1$$

- During the Maintenance Period (attributed to the treatment initiated in the Maintenance Period), the study medication duration algorithm specified for the Maintenance Period in Section 10.1.2 applies.

- Definitions for time at risk during the combined treatment period will be calculated as follows:

- For study participants who do not switch study treatments per study design:

- For study participants who complete the Maintenance Period as planned and continue into an open-label study (and, therefore, do not have the SFU visit in the feeder study):

$$\text{Date of last visit} - \text{Date of first dose} + 1$$

- For study participants who die prior to the final visit:

$$\text{Date of death} - \text{Date of first dose} + 1$$

- For all other study participants, use the minimum of the following:
 - $Date of last dose - Date of first dose + 140 + 1$
 - $Date of last clinical contact - Date of first dose + 1$

This last group could include study participants who discontinue early, study participants who complete the Maintenance Period as scheduled but choose not to continue into an open-label study, or study participants who are ongoing in the SFU period at the time of the data snapshot.

- For study participants who switch study treatments per study design:

- During the DBTP (attributed to initially randomized treatment):

$$Date of first dose (MP) - 1 - Date of first dose (DPTB) + 1$$

This assumes that any study participant in this category has completed the DBTP and doses [with a new study treatment] in the Maintenance Period.

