10.2 Adverse events

Adverse events with start date prior to first administration of study medication are defined as pre-treatment AEs. No summaries of these events will typically be produced although they will be included in listings.

Adverse events that started more than 140 days after the last administration of study medication are defined as post-treatment AEs. Such events will not be included in any tabulated summaries but will be listed.

Treatment-emergent AEs (TEAEs) are defined as those AEs that have a start date on or following the first dose of study treatment through the final dose of study treatment + 140 days (covering the 20-week SFU period).

All summaries will be provided by treatment group. The treatment group for each study participant will be defined as the treatment received at the onset of the AE. If the onset of the AE occurs on the day where the study participant switches treatment from the Double-Blind Treatment Period to the Maintenance Period and receives a new treatment, it will be attributed to the originally randomized study treatment. The only exception to this is if the AE fulfills the criteria for an anaphylactic reaction. See Section 3.7 for further details.

AEs will be presented as “number of study participants (percentage of study participants) [number of events]”. In this style of output, “[number of events]” will include all cases of an AE including repeat occurrences in individual study participants, while “number of study participants” will count each study participant only once.

Adverse event summaries by SOC, HLT and PT will be ordered alphabetically for SOC and HLT within SOC and in terms of decreasing frequency for PT within HLT in the bimekizumab treatment group and then similarly by decreasing frequency in the placebo group.

AE summaries by PT will be ordered in terms of decreasing frequency for PT within the bimekizumab treatment group, and in the event of ties, PT will be sorted alphabetically.

Study participant time at risk represents the time a study participant is at risk for having an AE. The definitions for study participant time at risk (in days) are outlined in Section 10.1. These definitions will be used for exposure-adjusted AE summaries.

Selected AE summaries will include the exposure adjusted incidence rate (EAIR) with associated 95% confidence interval and the exposure adjusted event rate (EAER).

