The EAIR is defined as the number of study participants (k) with a specific AE adjusted for the exposure and will be scaled to 100 subject-years:

$$\text{EAIR} = 100 \times \frac{k}{\sum_{i=1}^n (T_{\text{Exp}(i)})}$$

where n is the total number of study participants in the respective treatment group, and $T_{\text{Exp}(i)}$ is the time of exposure for each study participant defined as:

- For study participants with the specific AE of interest: years since first dose of the study treatment to the first occurrence for the AE of interest at the level of coding evaluated (see Section 10.1)
- For study participants without the AE: the time at risk in years (see Section 10.1)

Exact Poisson 95% confidence intervals for incidence rates are calculated using the relationship between the Poisson and the Chi-square distribution (Ulm, 1990; Fay and Feuer, 1997):

$$\begin{aligned} LCL &= \frac{\chi^2_{2n,\alpha/2}}{2} \\ UCL &= \frac{\chi^2_{2(n+1),1-\alpha/2}}{2} \end{aligned}$$

where n is the number of study participants with a specific AE for the incidence rate of interest and is the basis for the number of the degrees of freedom for the chi-square quantile for the upper tail probability χ^2 .

The EAER will be the number of AEs including repeat occurrences in individual study participants divided by the total time at risk scaled to 100 subject-years and calculated using:

$$\text{EAER} = 100 \times \frac{N_{AE}}{\sum_{i=1}^n (T_{\text{Risk}(i)})}$$

where N_{AE} is the total number of AEs, n is the total number of study participants and $T_{\text{Risk}(i)}$ is the time at risk in years for each study participant.

No confidence interval will be computed for EAER.

In the following sections, all tables based on “100 subject-years” will include EAIR (with 95% confidence interval) and EAER.

As previously indicated in [Table 4–3](#), the AE summary tables described in Section [10.2.1](#) and Section [10.2.2](#) will be presented:

- on the SS for the overall period, presenting the BKZ 160 mg Total treatment column only.
- on the SS for the Double-Blind Treatment Period for the Week 24 interim analysis only, presenting the Placebo and BKZ 160mg treatment columns.
- and on the MS for the Maintenance Period for the Week 52 interim analysis only, presenting the BKZ 160 mg Total treatment column only.

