10.2.1 Standard AE summaries

The following tabular summaries will be produced:

- Incidence of TEAEs – Overview.
- Incidence of TEAEs per 100 subject-years by SOC, HLT, and PT.
- Incidence of Serious TEAEs per 100 subject-years by SOC, HLT, and PT.
- Incidence of TEAEs Leading to Study Discontinuation per 100 subject-years by SOC, HLT, and PT.
- Incidence of TEAEs Leading to Study Drug Discontinuation per 100 subject-years by SOC, HLT, and PT.
- Incidence of TEAEs Leading to Death by SOC, HLT, and PT.
- Incidence of TEAEs by Relationship by SOC, HLT, and PT.
- Incidence of TEAEs by Intensity, SOC, HLT, and PT.
- Incidence of TEAEs by decreasing frequency of PT.
- Incidence of TEAEs Above Reporting Threshold of 5% by SOC and PT.
- Incidence of Non-Serious TEAEs Above Reporting Threshold of 5% by Relationship SOC and PT.
- Incidence of Related TEAES by SOC, HLT, and PT
- Incidence of Related TEAES Above Reporting Threshold of 5% by SOC and PT.
- Incidence of TEAEs per 100 subject-years by SOC, HLT, and PT and by Time of Onset Relative to Anti-bimekizumab Antibody Status. The table will include columns for the following:
 - TEAEs starting before the first ADAb positive result (includes ADA_b Categories 2 and 5) where TEAEs have occurred before the following events:
 - a) the first positive ADA_b result for study participants in category 2 and
 - b) the first post-Baseline boosted ADA_b titer result for study participants with titer results or the first post-Baseline positive ADA_b result for study participants with positive ADA_b at Baseline with no other samples with titer available for study participants in category 5.

- TEAEs starting on the same date or after the first ADAb positive result (includes ADAbs Categories 2, 3, 4, 5 and 6) where TEAEs have occurred on or after the following events:
 - a) the first positive ADAb results for study participants in categories 2, 3, 4 and 6, and
 - b) the first post-Baseline boosted ADAb titer result for study participants with titer results and the first post-Baseline positive ADAb result for study participants with positive ADAbs at Baseline with no other samples with titer available for study participants in category 5.
- TEAEs for study participants who are ADAbs negative at all time points (includes ADAbs Category 1).

Note: For TEAE by onset relative to ADAbs positivity status, all available ADAbs data at the time of IA cut-off will be utilized to derive the study participant-level ADAbs status categories.

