10.2.2 Other safety topics of interest summaries

The safety topics of interest (or AEs with special monitoring) for the bimekizumab program are:

- Infections (serious, fungal, opportunistic and tuberculosis)
- Malignancies
- Major adverse cardiac events (MACE)
- Neutropenia
- Suicidal Ideation and Behavior
- Inflammatory bowel disease
- Hypersensitivity (including anaphylactic reactions)
- Hepatic events and drug-induced liver injury (DILI)

The analyses produced for the TEAE of special monitoring are based on the specifications described in the Bimekizumab safety topic of interest document version from 26-Mar-2020.

Separate tables will be created to summarize each of the above AEs (except when notified) per 100 subject-years by system organ class, high level term, and PT.

Infections

The summary table for fungal infection will include all TEAEs (serious and non-serious) which code to the High Level Group Term “Fungal infectious disorders”.

Opportunistic infections (including tuberculosis) will be summarized in a stand-alone table and will include all opportunistic infection TEAEs identified as per the UCB-defined search criteria which were adjudicated as opportunistic infections (refer to [Appendix 2](#) for further details on the process for identifying opportunistic infections).

No dedicated table will be produced for serious infections, as there will be identified based on MedDRA classification (SOC “Infections and infestations”) using the “Any SAE” table specified in Section [10.2.1](#).

Fungal infections and opportunistic infections will be listed separately.

Malignancies

Two tables will be created on malignancies:

- one table will display all events in the criteria standardized MedDRA Query (SMQ)= “Malignant or unspecified tumors (SMQ)”,
- and another table will display all events in the criteria SMQ= “Malignant tumors (SMQ)”.

The SMQ search will include all TEAEs which code to a PT included in the Scope=Narrow group within each SMQ.

The output tables will include two different overall incidence rows:

- The first overall incidence row will summarize “Any Malignancy” and this row will summarize the incidence of all AEs flagged for inclusion in the table (using the appropriate SMQ depending on the table), regardless of the HLT it codes to.

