10.2.3 Extra-Articular Manifestations

A summary table will be presented on study participants having TEAE uveitis. The table will include all events defined by one of the following preferred terms: "Autoimmune uveitis", "Iridocyclitis", "Iritis", "Uveitis". The TEAE will be summarized per 100 subject-years by system organ class, high level term, and PT. The analysis will be stratified by study participants with or without a previous medical history of uveitis at Baseline. Study participants with uveitis at Baseline will be identified as the ones having documented an uveitis in the "Extra-articular Assessments form at Baseline" form ("Does subject have a history of uveitis?").

The analysis will be presented on the overall period as well as on the Double-Blind period.

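### The exact Poisson limits given for the EAIR are limits for a count: total exposure and the factor 100 are missing

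*SAP*

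**What the plan says.** Section 10.2 defines EAIR = 100 × k / ΣT_Exp(i), where k is the number of participants with the event. T_Exp runs to the first occurrence for those with the event and is the time at risk for everyone else. The section then states: "Exact Poisson 95% confidence intervals for incidence rates are calculated using the relationship between the Poisson and the Chi-square distribution". The limits follow:

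- LCL = χ²(2n, α/2) / 2
- UCL = χ²(2(n+1), 1−α/2) / 2

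The symbol is explained as "where n is the number of study participants with a specific AE for the incidence rate of interest". In the EAIR formula a few lines earlier, the same letter n is the total number of participants in the treatment group.

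The section also fixes where the interval appears: all tables based on 100 subject-years "will include EAIR (with 95% confidence interval) and EAER". This reaches:

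- Section 10.2.1: the tables of all TEAEs, of TEAEs leading to study or study drug discontinuation, of TEAEs by antibody status, and "Incidence of Serious TEAEs per 100 subject-years by SOC, HLT, and PT";
- Section 10.2.2: "Separate tables will be created to summarize each of the above AEs (except when notified) per 100 subject-years";
- Section 10.2.3, on uveitis: "The TEAE will be summarized per 100 subject-years by system organ class, high level term, and PT".

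**The concern.** The estimate is a rate per 100 subject-years, but the printed limits are on the scale of a count. They depend only on how many participants had the event, so the same count gives the same interval whatever the exposure. In the double-blind tables, a placebo row and a bimekizumab row with equal counts would carry identical intervals, although planned exposure differs two-fold.

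A table programmed to the formula as written could show rates lying outside their own confidence limits. No single mental correction would serve the reader, because the limits are too low in the double-blind tables and too high in the maintenance and overall tables.

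**Working it through.** The SAP gives a formula and no worked figure, so there is nothing to reproduce first.

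**What the printed limits are.** With L = χ²(0.025; 2k)/2 and U = χ²(0.975; 2(k+1))/2 as lower-tail quantiles, P(X ≥ k | mean L) = 0.025 and P(X ≤ k | mean U) = 0.025 for k = 1, 3, 5, 10, 20 and 40. For k = 0, L = 0 and the upper condition also gives 0.025. These are the exact limits for a Poisson mean count. The EAIR is the count times 100 / ΣT_Exp, so its limits are 100 × L / ΣT_Exp and 100 × U / ΣT_Exp. The two pairs coincide only when ΣT_Exp = 100.

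**Assumed exposure.** 200 bimekizumab (BKZ) and 100 placebo participants (Section 2.4), full dosing and follow-up, exposure not cut at the event, days / 365.25:

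- Double-blind, 112 days: BKZ 200 × 112 / 365.25 = 61.3; placebo 100 × 112 / 365.25 = 30.7.
- Maintenance: if all enter the extension, Week 52 − Week 16 + 1 = 253 days, and 300 × 253 / 365.25 = 207.8. If none enter, Week 48 − Week 16 + 140 + 1 = 365 days, and 300 × 365 / 365.25 = 299.8.
- BKZ Total, overall: if all enter, (200 × 365 + 100 × 253) / 365.25 = 269.1. If none enter, Section 10.1.3 applies to those who do not switch treatment ("Date of last dose - Date of first dose + 140 + 1", that is 336 + 140 + 1 = 477 days), and (200 × 477 + 100 × 365) / 365.25 = 361.1.

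**Intervals per 100 subject-years.**

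| Case | EAIR | As printed | Correct |
|---|---|---|---|
| BKZ double-blind, k = 20 | 32.6 | 12.2–30.9 | 19.9–50.4 |
| Placebo double-blind, k = 5 | 16.3 | 1.6–11.7 | 5.3–38.1 |
| BKZ Total overall, k = 10, 269.1 subject-years | 3.7 | 4.8–18.4 | 1.8–6.8 |
| BKZ Total overall, k = 10, 361.1 subject-years | 2.8 | 4.8–18.4 | 1.3–5.1 |

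In all four rows the printed interval excludes its own estimate.

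**Factor needed (100 / ΣT_Exp) and smallest k at which the printed limits exclude the EAIR.**

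| Period | Factor | Smallest k |
|---|---|---|
| BKZ double-blind | 1.63 | 16 |
| Placebo double-blind | 3.26 | 3 |
| Maintenance | 0.48 to 0.33 | 11 to 6 |
| BKZ Total overall | 0.37 to 0.28 | 7 to 5 |

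For participants who continue into maintenance, Section 10.1.1 gives 113 double-blind days. With 113 days the BKZ threshold becomes 17 and the placebo threshold stays at 3.

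**Coverage of the true rate**, summing Poisson probabilities with mean rate × exposure / 100 over the counts whose limits contain it:

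| Case | True rate | As printed | Correct |
|---|---|---|---|
| BKZ double-blind | 5 | 95% | 99% |
| BKZ double-blind | 20 | 57% | 97% |
| Placebo double-blind | 10 | 37% | 99% |
| BKZ Total overall, 269.1 subject-years | 5 | 21% | 96% |

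**Notation in the same lines.** The text calls the quantile one for an upper tail probability, but the printed subscripts work only as lower-tail probabilities. Read as upper-tail with k = 10, the lower limit is 17.1 and the upper 5.5. If n is taken from the EAIR formula as the group size of 200, the limits are 173.2 and 229.7.

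**The case against.** The strongest reply is that the formula is abbreviated rather than wrong. The section names the target (an incidence rate), the scale (100 subject-years), the denominator (ΣT_Exp) and the method. The omitted step is the one already applied to k a few lines above, and a programmer who knows the method would probably apply it. Intervals that miss their own estimates would also be noticed. This lowers the chance of wrong tables, but it does not mend the text: the SAP prints the scaling in full for both the EAIR and the EAER and gives limits without it, so double programming to the specification could reproduce the error.

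The consequence is limited, and that stands. The tables are descriptive. The between-arm risk differences for the safety topics (Section 10.2.2) have their own interval, and the counts, percentages and EAER are unaffected.

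The objection to the illustrations also stands in part. Section 10.2 stops T_Exp at the first event, so full exposure is an approximation that suits uncommon events. For a very common event the estimate can fall back inside the printed limits. With a constant hazard of 2.5 per year, 200 participants at 365 days and 100 at 253 days, exposure is about 106 subject-years, k about 266 and the EAIR 250, against printed limits of 235 to 300. That happens because exposure is then close to 100 subject-years. The coverage figures, likewise, hold only if nobody rescales.

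**Conclusion.** The formula is wrong as written. Its limits belong to the expected count and are off by the factor 100 / ΣT_Exp in every table per 100 subject-years, unless exposure happens to equal 100. On planned sizes and full follow-up, the factor needed runs from about 3.3 (placebo, double-blind) to about 0.28 (bimekizumab overall, nobody entering the extension). The exact thresholds and coverage figures rest on those assumptions and on exposure not being cut at the event; the defect does not. Because no test or decision rule uses these limits and the point estimate is sound, it should be fixed but does not threaten the trial's conclusions.

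**What to change.** In Section 10.2, replace the two limits by:

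- LCL = 100 × χ²(0.025; 2k) / (2 × ΣT_Exp), with LCL = 0 when k = 0
- UCL = 100 × χ²(0.975; 2(k+1)) / (2 × ΣT_Exp)

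State that the quantiles are lower-tail and delete the reference to an upper tail probability. Use k for participants with the event, as in the EAIR formula, and keep n for the group size. The cost is one formula and one symbol, with no new data or analysis.

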10.2.1 Standard AE summaries

The following tabular summaries will be produced:

- Incidence of TEAEs – Overview.
- Incidence of TEAEs per 100 subject-years by SOC, HLT, and PT.
- Incidence of Serious TEAEs per 100 subject-years by SOC, HLT, and PT.
- Incidence of TEAEs Leading to Study Discontinuation per 100 subject-years by SOC, HLT, and PT.
- Incidence of TEAEs Leading to Study Drug Discontinuation per 100 subject-years by SOC, HLT, and PT.
- Incidence of TEAEs Leading to Death by SOC, HLT, and PT.
- Incidence of TEAEs by Relationship by SOC, HLT, and PT.
- Incidence of TEAEs by Intensity, SOC, HLT, and PT.
- Incidence of TEAEs by decreasing frequency of PT.
- Incidence of TEAEs Above Reporting Threshold of 5% by SOC and PT.
- Incidence of Non-Serious TEAEs Above Reporting Threshold of 5% by Relationship SOC and PT.
- Incidence of Related TEAES by SOC, HLT, and PT
- Incidence of Related TEAES Above Reporting Threshold of 5% by SOC and PT.
- Incidence of TEAEs per 100 subject-years by SOC, HLT, and PT and by Time of Onset Relative to Anti-bimekizumab Antibody Status. The table will include columns for the following:
 - TEAEs starting before the first ADAb positive result (includes ADA_b Categories 2 and 5) where TEAEs have occurred before the following events:
 - a) the first positive ADA_b result for study participants in category 2 and
 - b) the first post-Baseline boosted ADA_b titer result for study participants with titer results or the first post-Baseline positive ADA_b result for study participants with positive ADA_b at Baseline with no other samples with titer available for study participants in category 5.

- TEAEs starting on the same date or after the first ADAb positive result (includes ADAbs Categories 2, 3, 4, 5 and 6) where TEAEs have occurred on or after the following events:
 - a) the first positive ADAb results for study participants in categories 2, 3, 4 and 6, and
 - b) the first post-Baseline boosted ADAb titer result for study participants with titer results and the first post-Baseline positive ADAb result for study participants with positive ADAbs at Baseline with no other samples with titer available for study participants in category 5.
- TEAEs for study participants who are ADAbs negative at all time points (includes ADAbs Category 1).

Note: For TEAE by onset relative to ADAbs positivity status, all available ADAbs data at the time of IA cut-off will be utilized to derive the study participant-level ADAbs status categories.

The following summary tables will be produced to support results disclosure activities

- Incidence of Serious TEAEs by Relationship SOC, HLT, and PT
- Incidence of TEAEs Leading to Death by Relationship by SOC, HLT, and PT
- Incidence of Non-Serious TEAEs Above Reporting Threshold of 5% (in any treatment group, and in any study period) by SOC and PT

By-study participant listings on all AEs and all deaths will be provided on the enrolled set. Serious AEs and AEs leading to study discontinuation will also be listed on the safety set. AEs occurring on the day of first study drug administration will also be listed on the randomized set. For study participants randomized to Placebo, this will include AEs occurring at first administration of Bimekizumab at Week 16. A glossary listing will also be created for all TEAEs.

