9.2.1.3 Definition of ADAb Categories

In addition, the anti-BKZ antibody status will be further classified as outlined below:

- **Pre ADAb negative – treatment emergent ADAb negative (Category 1):** Includes study participants who are negative at Baseline and antibody negative at all sampling points (including SFU), one post-Baseline missing/inconclusive sample is allowed for study participants with pre-ADAb negative sample. This group also includes study participants who have a missing/inconclusive pre-treatment sample (eg, either missing/inconclusive or insufficient volume) at Baseline with all post-Baseline samples as ADAb negative.
- **Pre ADAb negative – treatment emergent ADAb positive (Category 2):** Includes study participants who are ADAb negative at Baseline and ADAb positive at any sampling point post treatment (including SFU). This group also includes study participants who have a missing pre-treatment sample (either missing or insufficient volume) at Baseline with one or more ADAb positive post-treatment samples.
- **Pre ADAb positive – treatment emergent reduced ADAb (Category 3):** Includes study participants who are ADAb positive at Baseline, and antibody negative at all sampling points post-treatment (including SFU).
- **Pre ADAb positive – treatment emergent unaffected ADAb positive (Category 4):** Includes study participants who are positive at Baseline and are positive at any sampling

point post-treatment (including SFU) and all post-Baseline samples have titer values < 2.07 times the Baseline titer (where 2.07 is Minimum Significant Ratio (MSR))

- **Pre ADA_b positive – treatment emergent ADA_b boosted positive (Category 5):** Includes study participants who are positive at Baseline and have at least one positive post-treatment sample (including SFU) that has titer value ≥ 2.07 times the Baseline titer (where 2.07 is Minimum Significant Ratio (MSR))

Note: For any study participant who is positive at Baseline and positive at a post-Baseline time point, but for whom titers are not available to determine treatment unaffected or treatment boosted status, the study participant will be considered as treatment boosted (ie,, Category 5), assuming no other samples are available.

- **Inconclusive (Category 6):** Includes study participants who have a positive pre-treatment sample and some post-treatment samples are missing/inconclusive, while other post-treatment samples are ADA_b negative.

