- **Total treatment-emergent (Category 7 [Categories 2 and 5 combined]):** Includes study participants who are pre ADA_b negative – treatment emergent ADA_b positive (Category 2) and pre ADA_b positive – treatment boosted ADA_b positive (Category 5).
- **Total prevalence of pre-ADA_b positivity (Category 8 [Categories 3, 4, 5 and 6 combined]):** Study participants that are tested ADA_b positive at Baseline.
- **Missing (Category 9):** Includes study participants who have a negative or missing/inconclusive pre-treatment sample at Baseline and more than one post-treatment samples are missing/inconclusive, while other samples are ADA_b negative. Includes also study participants who have missing/ inconclusive pre-treatment sample at Baseline, and only one missing post-baseline sample with no ADA_b positive.

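### The table of adverse events by antibody onset uses two switch rules for participants who are all antibody positive at Baseline, so its before and after columns are not like for like

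*SAP*

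**What the plan says.** SAP Section 10.2.1 lists a table of TEAEs per 100 subject-years with three columns defined by antibody status.

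- The first is headed "TEAEs starting before the first ADAb positive result" and takes Categories 2 and 5. For Category 2 the switch is the first positive result. For Category 5 it is "the first post-Baseline boosted ADA_b titer result for study participants with titer results or the first post-Baseline positive ADA_b result", the latter for participants without usable titers.
- The second is "TEAEs starting on the same date or after the first ADAb positive result (includes ADAbs Categories 2, 3, 4, 5 and 6"). Its switch date is "the first positive ADAb results for study participants in categories 2, 3, 4 and 6"; for Category 5 it is again the boosted titer or its substitute.
- The third is Category 1, negative throughout.

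The categories come from SAP Section 9.2.1.3. Category 3: "Includes study participants who are ADAb positive at Baseline, and antibody negative at all sampling points post-treatment (including SFU"). Category 4 is positive at Baseline and at some later point, but "all post-Baseline samples have titer values < 2.07 times the Baseline titer". Category 5 is positive at Baseline and reaches at least 2.07 times the Baseline titer at least once. Category 6 is positive at Baseline, with later samples either missing or inconclusive, or negative. The section also defines Category 7 (total treatment-emergent) as 2 plus 5, and Category 8 (all positive at Baseline) as 3, 4, 5 and 6.

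**The concern.** The table is there to show whether adverse events follow antibody formation. That needs one definition of the moment at which a participant crosses from before to after. Here the crossing point depends on the category, and the category depends on what happens later. Two Baseline-positive participants with the same unboosted titer on the day of an event go to opposite columns, according to whether one of them is boosted afterwards.

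The after column also mixes events following newly formed or boosted antibodies with events in people whose antibodies were there before treatment and never rose, or were not detected again. A reader comparing the two columns would be looking at different mixtures of participants as well as different times, and could not isolate events that follow treatment-emergent antibodies.

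**Working it through.** The SAP states no figure on this point, so there is none to reproduce. The check traces each category through the column rules.

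**Inputs.** Category definitions: SAP 9.2.1.3. Column rules and switch dates: SAP 10.2.1. TEAE window, from first dose to final dose plus 140 days: SAP 10.2.

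**Step 1: when is the first positive result?** For Categories 3 to 6 it is the Baseline sample. TEAEs start on or after first dose, so every TEAE in these four categories falls on or after the first positive result.

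**Step 2: compare the planned columns with each possible single rule.**

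| Category | Baseline | After Baseline | As planned | Rule A: first positive | Rule B: treatment-emergent positivity |
|---|---|---|---|---|---|
| 2 | negative or missing | turns positive | before, then after | before, then after | before, then after |
| 3 | positive | negative at every sample | all after | all after | never switches |
| 4 | positive | positive, never boosted | all after | all after | never switches |
| 5 | positive | boosted at least once | before until boost, then after | all after | before until boost, then after |
| 6 | positive | no positive sample | all after | all after | never switches |

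The plan agrees with Rule A everywhere except Category 5, and with Rule B everywhere except Categories 3, 4 and 6. No single rule gives the planned columns.

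**Step 3: the same state in two columns.** Baseline positive and below 2.07 times the Baseline titer is *after* in Category 4 and *before* in Category 5. For Category 5 the heading of the before column is untrue, since the first positive result was at Baseline.

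**Step 4: who is in each column.** Before: 2 and 5. After: 2 and 5, plus 3, 4 and 6, which contribute no before time.

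**Step 5: can a size be given?** Only under assumptions from outside the SAP. Leave Category 5 aside. Let e be the share of participants in Category 2, with half their time after onset; b the share in Categories 3, 4 and 6; 1.5 the event-rate ratio after treatment-emergent antibodies; and r the ratio in Categories 3, 4 and 6, all relative to the before rate. With person-time split at the switch date:

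apparent ratio = (0.5e × 1.5 + b × r) / (0.5e + b)

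With e = 0.30 and b = 0.10 the denominator is 0.15 + 0.10 = 0.25, and:

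- r = 1.0: (0.225 + 0.100) / 0.25 = 1.30
- r = 1.5: (0.225 + 0.150) / 0.25 = 1.50
- r = 2.0: (0.225 + 0.200) / 0.25 = 1.70

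The mixture can lower, leave or raise the ratio, depending on r. The SAP gives no value for e, b or r, and Sections 10.1 and 10.2 state no split of time at risk at the antibody date.

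**The case against.** The strongest defence is that the placement is deliberate. Section 10.2.1 names every included category and gives each a switch date, so the table can be programmed. For Categories 3, 4 and 6 the after heading is literally true, because these participants were positive at Baseline. Section 9.1.2 uses a similar convention for the PK summaries: once positive, a participant stays positive whatever later samples show. The table is one descriptive output among many, and individual antibody results and all adverse events are listed as well.

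Much of this stands. A reader might infer that the after heading is false for Category 3; it is not, although the grouping obscures what the table should show. A reader might infer that the two columns hold different people; in fact the before categories are a subset of the after categories, and the difference is the addition of 3, 4 and 6. A reader might infer that a real increase in events must be diluted; Step 5 shows that this follows only if pre-existing, unboosted antibodies carry no extra risk, which the SAP does not say. Category 9 has no column, but its participants have no positive sample and "more than one post-treatment samples are missing/inconclusive, while other samples are" negative, or a similar gap at Baseline, so they fit none of the three. That is an omission, not an error.

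The defence does not reach Category 5. An ever-positive convention would put all its events in the after column, and the plan does not.

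**Conclusion.** The point holds as an internal inconsistency in Section 10.2.1. Two switch rules are applied to participants who are all Baseline positive, the same antibody state lands in opposite columns for Categories 4 and 5, and the before heading is wrong for Category 5. Adding Categories 3, 4 and 6 to the after column alone means that before and after are not like for like. This rests only on the SAP's own definitions.

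Neither size nor direction of the effect on the reported rates can be given, because the SAP states no antibody frequencies; if Baseline positivity is rare, the effect is small. The table is descriptive and has no bearing on the primary or key secondary inference. It should still be corrected, because its purpose is the before-after reading that the mixed rule undermines.

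**What to change.** Use treatment-emergent positivity as the only switch. The SAP already has it as Category 7 and uses it in Section 9.2.2.1 for the first-occurrence table and the time-to-positivity figure. The columns become:

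- (a) Before treatment-emergent ADAb: Categories 2 and 5, before the first positive result (2) or the first boosted result (5). For Category 5 without titers, the first post-Baseline positive result.
- (b) On or after that date: Categories 2 and 5.
- (c) Baseline positive, not boosted: Categories 3, 4 and 6, with Category 4 shown apart from 3 and 6 if numbers allow.
- (d) Category 1.

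A column for Category 9 is optional. State the Category 5 switch once for both columns; the two sub-bullets now join its alternatives differently (*or* in one, *and* in the other).

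The cost is SAP wording and one column more than planned, or two if Category 4 is separated, plus one if Category 9 is shown. All are built from existing categories and need no new data. The downside is small numbers in column (c).
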